#### Subject Withdrawal from the Registry

Subjects who are alive at the time of their enrollment in the registry can withdraw from the registry without indicating any reasons at any time. No additional data will be collected and reported into the registry database after consent withdrawal. The sponsor may retain and continue to use any data collected before the withdrawal of consent, if not explicitly requested otherwise by the subject.

A replacement subject may be enrolled in the rare event that a subject decides to withdraw from the registry before all follow-up visits have been recorded in the EDC.

#### Subject Lost to Follow Up

No subject lost to follow up are expected in this registry. According to General Exclusion criterion #1, subjects with no follow-up after treatment should not be included in the registry. All subjects that complete at least one follow-up after treatment will be enrolled.

#### Subject Registry Completion

A subject has completed the registry when all expected follow-up visits have been completed and properly recorded in the EDC. Any subject who does not complete these requirements due to voluntary withdrawal, physician withdrawal, death, or any other reason will be considered a withdrawal.

#### Subject Discontinuation

Subjects will be discontinued from the registry in case of the explant of the device or, for subjects enrolled in the AV access cohort, renal transplantation.

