### 5.2. Informed Consent Process

For the inclusion of patients in the registry, the investigator should review all inclusion/exclusion criteria and, in the case of including patients who are alive and reachable at the site, the patient will be required to sign the Informed Consent Form (ICF) before enrolment in the registry.

As this study is retrospective and considering the nature of patient's disease, some patients may have died by the time they are included. The investigator is expected to make reasonable efforts to contact the potential patient, such as checking whether they are still alive, browsing through their clinical records, contacting available telephone numbers, or obtaining contact information from population and/or health care registers. If, after reasonable effort, the patients are found to be deceased or not reachable, the request for informed consent can be waived in accordance with national and local legislation.

If, during the course of the registry, patients who were not previously reachable come back to the clinical site for a visit, the investigator is expected to collect informed consent from those patients.

To protect patient privacy, patient-identifiable information (e.g., name, initials, complete birth date, and race) will not be collected.

The informed consent form will include emergency contact details for any concerns. The case history (i.e., source documents / subject chart) for each subject shall document that such informed consent was obtained, if this was obtained remotely or if the consent was waived. In case the consent was waived, the reason must be clearly described in the source document.

The EC approved consent form will be signed and personally dated by the subject and the person who conducted the informed consent discussion. The original signed informed consent form will be retained in the subject records. A copy of the signed informed consent document will be given to the subject for their records.

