### 5.8.2. Data Elements

The following clinical routine data will be recorded in the registry database from the existing medical records of enrolled subjects.

- Subject information and Demographics (Age and sex)
- Medical History
- Index procedure information
- Discharge information
- Follow-up data, including (antiplatelet and anticoagulant therapy) and imaging reports (no imaging will be collected)
- Adverse events
- Device Deficiency
- Repeat Intervention
- Death or discontinuation

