### 5.10. Follow Up

No on-site follow-up is required after the subject is included in the registry, as the registry consists of retrospective data collection only.

Follow-up data will be collected from the information already present in the medical chart at least to 5 years from the index procedure for the PAD and aortic aneurysm cohort and at least to 2 years for the dialysis access cohort. This data should include any adverse events, repeat interventions, and records of office, telephone, or imaging visits. No imaging will be collected for this registry.

In case the site recognized that the enrolled subject does not have data available regarding the last FU visit specified in the protocol, site should enter the next follow up data available (i.e. if a patient did not come in at year 5, but came in at year 6, year 6 data should be entered). If no follow up visit data is available, site staff should collect and document any past safety data (SAE, re-intervention, hospitalization, death, etc.) through the end of the follow up period specified for the cohort. If consent is waived, the site should contact relatives or general practitioner by phone to collect this data.

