### 5.13.1. Subject Discontinuation

Subjects will be discontinued from the registry in case of the explant of the device or renal transplantation for subjects enrolled in the AV access cohort.

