### 9.1.3. Adverse Event Reporting and Coding

health is not considered serious.

Considering the retrospective nature of the registry only AEs already documented in the subject's medial record will be reported on the appropriate CRF.

No follow-up related to the open adverse event in order to obtain new information is required for this registry.

The investigator at each site is ultimately responsible for reporting AEs to the sponsor.

The following information on each reported AE will be collected:

- Adverse event name
- Adverse event onset date
- Relationship
- Classification serious or non-serious
- Outcome
- Resolution date

Adverse events will be coded using the Medical Dictionary for Regulatory Activities (MedDRA).

Adverse event submission guidelines:

- Adverse event reporting begins once the patient is enrolled in the registry (ICF signed or waived). All adverse events should be reported from index procedure through registry completion / discontinuation.
- Provide a diagnosis if possible. If unable to provide a diagnosis, report the symptoms as separate events. Adverse events should be reported using the full name without abbreviations or narratives.
- Adverse events ongoing at registry completion / discontinuation should be left as "ongoing" on the AE case report form.
- Medical condition and adverse event observed at the time of treatment will be part in the medical history of the patients. Adverse events will be reported in the EDC only if they become serious or increase in intensity, or if a worsening of a baseline condition.

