## 9.1.4. Subject Death

In this registry, death is not considered an AE, but rather the outcome of an AE. An ongoing AE at the time of death or registry withdrawal will remain categorized as ongoing.

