#### Follow Up

No on-site follow-up is required after the subject is included in the registry, as the registry consists of retrospective data collection only. Follow-up data will be collected from the information already present in the medical chart for at least 5 years from the index procedure for the PAD and aortic aneurysm cohort and at least to 2 years for the dialysis access cohort. This data should include any adverse events, repeat interventions, and records of office, telephone, or imaging visits. No imaging will be collected for this registry. In case the site recognized that the enrolled subject does not have data available regarding the last FU visit specified in the protocol, site should enter the next follow up data available (i.e. if a patient did not come in at year 5, but came in at year 6, year 6 data should be entered). If no follow up visit data is available, site staff should collect and document any past safety data (SAE, re-intervention, hospitalization, death, etc.) through the end of the follow up period specified for the cohort. If consent is waived, the site should contact relatives or general practitioner by phone to collect this data.

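### Discontinuing subjects at device explant is not reconciled with follow-up to the cohort horizon, so later deaths and amputations may be lost from aortic survival and the PAD limb endpoints

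*SAP*

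**What the plan says.** **When participation ends.** The discontinuation paragraph of SAP 4.0 reads: "Subjects will be discontinued from the registry in case of the explant of the device or, for subjects enrolled in the AV access cohort". The event that this last clause introduces is renal transplantation. The punctuation confines only transplantation to the access cohort, so explant applies to all three. Protocol 5.13.1 has the rule without those commas, "explant of the device or renal transplantation for subjects enrolled in the AV access cohort", and can be read as confining both events to the access cohort.

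**What stops then.** Protocol 9.1.3: "All adverse events should be reported from index procedure through registry completion / discontinuation".

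**How far collection runs.** Protocol 5.10 takes data from the "medical chart at least to 5 years from the index procedure for the PAD and aortic aneurysm cohort". Where visit data are missing, sites are to document past safety information, including serious events and deaths, to the end of the cohort's period. SAP 4.0 (Follow Up) repeats this and adds: "If consent is waived, the site should contact relatives or general practitioner by phone to collect this data". Neither section mentions explant.

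**Who is analysed.** Protocol 10.6.2 puts every eligible enrolled subject into the primary and secondary endpoint analyses; the SAP's own population section does not repeat that sentence. SAP 5.0 leaves out subjects whose outcome is missing, and SAP 8.1 lists Kaplan-Meier tables without a censoring rule for explant.

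**The endpoints.** SAP Table 1 defines survival as all-cause, limb salvage by amputation above the ankle of the index limb, and amputation-free survival by that amputation or death. None requires the graft to be in place.

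**The concern.** An explant is plausibly linked to a bad course, such as infection or graft failure. Ending observation there is then outcome-related: the subjects cut off are not a random sample of those still at risk. A Kaplan-Meier estimate censored at explant is too high if risk rises afterwards. A complete-case proportion can move either way, because it loses later survivors as well as later deaths.

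Take an aortic subject explanted in year 2 who dies in year 3. Protocol 5.10 and 10.6.2 suggest that the death is collected and counted. The discontinuation rule suggests that the record closes in year 2, after which the subject could be censored there or treated as missing. The result should not depend on which section the site or programmer follows.

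The exposure is uneven. Aortic 5-year survival is a primary safety outcome. The two PAD endpoints are secondary and run to 1 year, so only explants in the first year matter to them.

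**Working it through.** **Plan's own figure.** The exact (Clopper-Pearson) 95% half-width for 21/65, about 32%, is 11.9 points, which reproduces the stated target of below 12. For 21/64 it is 12.05, so the aortic size has almost no slack for an excluded subject.

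**Inputs.** From the documents: aortic 5-year survival 33% (SAP Table 2), 65 aortic subjects, 72 per PAD population. Assumed, because the documents give no values: a share e of 2-5% explanted, a post-explant hazard ratio HR of 1-3, and PAD 1-year amputation-free survival of 85%.

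**Model.** Constant hazards over horizon τ.

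- Event hazard before explant: λ = -ln(S0)/τ.
- Explant hazard μ solves μ/(μ+λ) × (1 - exp(-(μ+λ)τ)) = e.
- Never explanted and event-free at τ: A = exp(-(λ+μ)τ).
- Explanted and event-free at τ: I = ∫₀^τ μ exp(-(λ+μ)t) exp(-HR·λ(τ-t)) dt.
- True value: S = A + I.
- If nothing is known after explant, Kaplan-Meier gives exp(-λτ) = S0 and the complete-case proportion is A/(1-e).

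**Aortic, S0 = 0.33, τ = 5.** λ = 0.2217. For e = 0.05, μ = 0.0171, A = 0.3029 and the complete-case value is 0.3029/0.95 = 0.3189.

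| e | HR | True S | Kaplan-Meier shift (points) | Complete-case shift (points) |
|---|---|---|---|---|
| 2% | 1 | 0.3300 | 0 | -0.4 |
| 2% | 2 | 0.3257 | +0.4 | 0.0 |
| 2% | 3 | 0.3235 | +0.7 | +0.2 |
| 5% | 1 | 0.3300 | 0 | -1.1 |
| 5% | 2 | 0.3192 | +1.1 | 0.0 |
| 5% | 3 | 0.3136 | +1.6 | +0.5 |

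The table treats every explanted subject as unknown, which is the upper bound on the number affected. With half unknown, the ranges shrink to 0 to +0.8 (Kaplan-Meier) and -0.5 to +0.3 (complete case).

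**PAD amputation-free survival, S0 = 0.85, τ = 1.** Here the 5% is assumed to be explanted within one year, a much higher explant hazard than in the aortic case. A = 0.8040. At HR = 3, S = 0.8432, Kaplan-Meier 0.8500 (+0.7) and complete case 0.8463 (+0.3). At HR = 1 the shifts are 0 and -0.4. Expected post-explant events per 72 subjects run from 0.1 (2%, HR 1) to 0.8 (5%, HR 3). If 2-5% were a 5-year figure, all of these would be smaller.

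**The case against.** The strongest reply is that the plan mostly answers the question already.

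- Protocol 10.6.2 has no explant exception, and the footnote to the table in 4.1 keeps subjects who died before the end of follow-up.
- Protocol 5.11 bars further data only after consent is withdrawn. Section 5.13 labels any non-completer a withdrawal, but that does not make explant a withdrawal of consent.
- Protocol 9.1.4 says "death is not considered an AE, but rather the outcome of an AE", so the cut-off in 9.1.3 does not by itself stop a death being recorded. Section 5.8.2 has a separate element, "Death or discontinuation", and SAP 8.2 lists deaths.
- For "patients who are alive and reachable at the site, the patient will be required to sign the Informed Consent Form (ICF) before enrolment", consent comes at least 5 years after an aortic or PAD implant, so survival to the horizon is known for them.
- SAP 7.0 sends derivation rules to dataset specifications that are not in these documents. The analysis is descriptive, so no test result turns on a shift of a point or so.

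Most of this stands, and it rules out three stronger readings. A reader might infer that the documents are silent on status after explant; they are not, since 5.10 and 10.6.2 both bear on it. A reader might infer that known post-explant deaths are to be discarded; no section directs that, because SAP 5.0 drops only missing outcomes and a known death is not missing. A reader might also infer from 5.8.2 that limb status is not collected. That list gives broad categories and names no patency item either, so the omission shows little.

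What remains is that none of these sections says it overrides the discontinuation rule. The data element does not say whether a death after discontinuation is entered. Status may stay unknown for unreachable subjects with waived consent. A year-1 amputation after explant falls outside the 9.1.3 reporting window.

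**Conclusion.** The point holds as an unreconciled set of rules. SAP 4.0 ends participation at explant in every cohort and protocol 9.1.3 then ends adverse event reporting; protocol 5.10, SAP 4.0 (Follow Up) and protocol 10.6.2 point the other way. Followed literally, the discontinuation rule produces outcome-related censoring in one primary safety outcome and two secondary endpoints.

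Its size cannot be derived from the documents. Under the assumptions above it is at most about +1.6 points for aortic Kaplan-Meier survival, -1.1 to +0.5 for the complete-case proportion, and under 1 point for PAD. All are small against the planned half-width of about 12 points. This is a cheap improvement worth making, not a threat to the registry's conclusions.

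**What to change.** In protocol 5.13.1 and SAP 4.0 (Subject Discontinuation), state that explant ends device-patency follow-up only, and that vital status and index-limb status continue to be abstracted from existing records to the cohort horizon. Give the two sections the same wording on which cohorts each event covers. Align 9.1.3 with 5.10 and SAP 4.0 (Follow Up), and say that a death after discontinuation is still entered. In SAP 5.0, state that explanted subjects stay in the survival, limb-salvage and amputation-free-survival analyses using their post-explant status.

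Abstracting all adverse events after explant, and stating that explant counts as loss of patency, would be tidy but are not needed for this point.

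The cost is a short wording amendment and some extra chart abstraction. At an assumed 2-5% explanted, that is about 1 to 3 of 65 aortic subjects (65 × 0.02 = 1.3; 65 × 0.05 = 3.25) and 1 to 4 of 72 in each PAD population (72 × 0.02 = 1.4; 72 × 0.05 = 3.6). Some later status may not be in the site chart and will stay missing.

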#### **Explant Procedures**

Not applicable due to the retrospective data collection.

#### 4.1 Clinical Event Committee

Not applicable due to the retrospective data collection.

#### 5.0 Statistical Analyses

No formal statistical hypothesis is planned for testing in the study. Separate primary and secondary outcomes will be measured along with two-sided 95% confidence intervals separately for each cohort using Exact Binomial method.

#### i. Timing of Analyses

Separate analysis will be performed for each of the PAD, Aortic Aneurysms and Dialysis Access cohorts once all data has been entered and cleaned in the EDC. Analyses at any other time may be performed at the discretion of Gore. There are no planned interim analyses or guidelines for early termination due to the retrospective and exploratory nature of the study.

#### ii. Analysis Populations

This study consists of five different analyses populations, defined by indication/disease type and device used. Separate analysis will be performed for each patient population.

- a. PAD patients treated with any
- b. PAD patients treated with
- c. Aortic Aneurysm patients treated with any
- d. Dialysis Access patients treated with any
- e. Dialysis Access patients treated with any
- iii. Pooling of Data

Clinical use is not expected to differ significantly between study sites. As such, there is no anticipated concern in pooling the data from different sites for analysis. However, separate analysis will be performed to show the consistency of safety and effectiveness by gender and age for the primary outcomes.

i) Statistical Analysis of Primary Endpoint(s)

Analysis for the primary endpoints will be presented with confidence intervals. Subjects with missing information on the primary outcomes will not be included in the analysis for the primary endpoint.

ii) Statistical Analysis of Secondary Endpoint(s)

Analysis for the secondary endpoints will be presented with confidence intervals. Subjects with missing information on these outcomes will not be included in the analysis.

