# 10.3. Sample Size Determination

The sample is calculated assuming the Binomial Exact 95% confidence interval would be constructed for the primary outcomes using the above assumptions. The subjects for which the primary outcomes cannot be determined will be considered missing in the analysis.

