### 10.6.2. Analysis Populations

This study consists of five different analyses populations, defined by indication/disease type and device used. Separate analysis will be performed for each patient population.

1.	PAD patients treated with any
2.	PAD patients treated with any
3.	Aortic Aneurysm patients treated with any
4.	Dialysis Access patients treated with any
5.	Dialysis Access patients treated with any

All enrolled subjects meeting the inclusion / exclusion criteria will be included in the primary and secondary endpoint analyses.

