# 10.6.4. Statistical Analysis of Primary Endpoint(s)

Analysis for the primary endpoints will be presented with confidence intervals. Missing data at the time of analysis will not be imputed.

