#### 2.5 Statistical Hypotheses

No formal statistical hypothesis is planned for testing in the study. Separate primary and secondary outcomes will be measured along with 95% confidence intervals for each cohort using Exact Binomial method. The analysis of the primary endpoint will be descriptive in nature.

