# 7.0 Analysis Specifications

SAS Analysis Dataset Specifications

- A specifications document is created following the template defined in MD146539 Work Instructions for Analysis Data Set (ADS) and MD146540 Analysis Data Set (ADS) Template for each analysis data set with at least the following details:
- Variable name
- Format
- Label
- Input variables and derivation rules

Statistical Output Specifications

- A specifications document is created in accordance with the corresponding template that contains at least the following details:
- Title and footnote
- Column headers
- Row labels for tables
- Cell formats
- Datasets and variables used with derivation details
- Revision history

Verification Level for Statistical Output

- All Analysis Datasets Level I
- All Tables Level I
- All Listings Level II

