# 8.0 Data Sets, Tables, Figures, and Listings

This section includes a list of the minimal planned statistical outputs, including tables, listings and figures which are to be created for the regulatory reports defined in the protocol. A different selection of tables, listings, and figures can be created for all other reporting efforts (Annual Reports etc.) as deemed necessary.

- 8.1 Analysis Tables
  - Summary of Subject Demographics by cohort
  - Summary of Medical History by cohort
  - Summary of concomitant medication by cohort
  - Summary of procedural details and assessments by cohort
  - Summary of discharge details by cohort
  - Summary of the devices used by cohort
  - Summary of follow-up, subject availability by visit with counts and percentages.
  - Kaplan-Meier estimate of the Device-related seroma or infection through 5 years in the PAD cohort
  - Kaplan-Meier estimate of the Secondary Patency (revascularization) through 5 years in the PAD cohort
  - Kaplan-Meier estimate of Survival through 5 years in the AA cohort
  - Kaplan-Meier estimate of the Primary Patency through 5 years in the AA cohort
  - Kaplan-Meier estimate of the Device-related infection through 2 years in the DA cohort
  - Kaplan-Meier estimate of the Useable access circuit(reported as secondary patency) through 2 years in the DA cohort
  - Kaplan-Meier estimate of the Limb Salvage through 1 year in the PAD cohort
  - Kaplan-Meier estimate of the Amputation-free survival through 1 year in the PAD cohort
  - Kaplan-Meier estimate of the Device-related Adverse Events through 1 year in the PAD cohort
  - Kaplan-Meier estimate of the Device-related infection requiring reoperation through 5 year in the PAD cohort
  - Kaplan-Meier estimate of the Primary Patency through 1 year in the PAD cohort

- Kaplan-Meier estimate of the Device-related Adverse Events through 1 year in the DA cohort
- Kaplan-Meier estimate of the Primary Patency through 1 year in the DA cohort
- Summary of the Device-related SAEs by cohort
- Summary of the Device-related death by cohort
- Summary of the procedure-related death by cohort
- Summary of the procedure-related SAE by cohort
- Summary of Repeat Interventions by cohort
- Summary of Freedom from Limb Salvage by cohort
- Summary of Device or Procedure Related Serious Adverse Events by cohort
- Summary of Adverse Events by MedDRA SOC, HLT, PT and Follow-up Interval (Number of Subjects, Number of Subjects with AEs, Number of AEs, at Procedure) by cohort

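### Exact binomial and Kaplan-Meier are both planned for all 13 endpoints, with no ranking and no rule for event-free death, transplant or explant, so the primary performance results are not uniquely defined

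*SAP*

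**What the plan says.** **Method.** Protocol 10.1 and SAP 2.5 name the exact binomial, and SAP 5.0 repeats it: "Separate primary and secondary outcomes will be measured along with two-sided 95% confidence intervals separately for each cohort using Exact Binomial method". The sample size rests on the same interval (protocol 10.3, SAP 2.7). SAP 2.5 adds: "The analysis of the primary endpoint will be descriptive in nature".

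**Who is analysed.** SAP 5.0 i) leaves subjects out: "Subjects with missing information on the primary outcomes will not be included in the analysis for the primary endpoint". SAP 5.0 ii) does the same for secondary endpoints. Protocol 10.3 says: "The subjects for which the primary outcomes cannot be determined will be considered missing in the analysis". Protocol 10.6.4 says: "Missing data at the time of analysis will not be imputed". Protocol 10.6.2, however, says: "All enrolled subjects meeting the inclusion / exclusion criteria will be included in the primary and secondary endpoint analyses".

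**Planned tables.** SAP 8.1, presented as a minimum list, has for example "Kaplan-Meier estimate of the Secondary Patency (revascularization) through 5 years in the PAD cohort". It holds a Kaplan-Meier line for every endpoint and no binomial table for any of them.

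**Early exits.** Subjects who die before the end of follow-up stay in the registry (protocol 4.1), and death is classed as a withdrawal (protocol 5.13, SAP 4.0). Follow-up stops at explant and, in the dialysis cohort, at renal transplant (protocol 5.13.1, SAP 4.0). No outcome or censoring rule is attached to any of these. SAP 7.0 defers "Input variables and derivation rules" to a separate specifications document.

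**The concern.** The two methods agree when every subject reaches the horizon or fails first. They differ once some subjects leave event-free, and in these populations such exits are expected: protocol 5.2 anticipates deaths, and the aortic cohort is planned on 5-year survival of at least 33%.

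Under the binomial the status of these subjects is also open. A patient who dies at year 2 with a working graft could be missing, a success or a failure. Under Kaplan-Meier the same patient would normally be censored, but the SAP does not say so. The report could present any of these as the cohort's primary performance result, and the choice could be made with the data in hand. In a descriptive study the estimate and its interval are the whole result. SAP 2.1 also ties the sample sizes to safety and performance acceptance criteria, so a shift of several points can change how the result is read.

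**Working it through.** **1. The plan's own figures.** Two-sided 95% Clopper-Pearson half-widths: n = 72 gives 11.97% at 55% and 11.94% at 56%; n = 65 gives 11.88% at 32% and 11.97% at 33%. The smallest n for 12% is 72 at 55% and 56%, and 65 at 33%. The planned sizes reproduce, on the condition that every subject is evaluable.

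**2. Endpoint count.** Two primary endpoints in each of three cohorts (6), five PAD secondary and two dialysis secondary: 13. SAP 8.1 matches them one for one.

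**3. One PAD dataset under each reading.** S = 0.56 comes from SAP Table 2. The exit probability e by year 5 is an assumption, because the documents give none. Event and exit hazards are taken as constant and independent.

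- λ = −ln(S), μ = −ln(1 − e)
- event-free at the horizon: J = S(1 − e)
- observed failures: F = λ/(λ+μ) × (1 − J)
- event-free exits: X = 1 − J − F

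At e = 30%: λ = 0.5798, μ = 0.3567, J = 0.392, F = 0.619 × 0.608 = 0.376, X = 0.232.

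- Excluded: J/(J+F) = 0.392/0.768 = 51.0%
- Counted as successes: J + X = 62.4%
- Counted as failures: J = 39.2%
- Kaplan-Meier, exits censored: 56% in the limit

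Exclusion by exit rate, with the coverage of the exact interval for the true 56%:

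| e | Exclusion reads | Gap to Kaplan-Meier | Evaluable of 72 | Half-width | Coverage |
|---|---|---|---|---|---|
| 10% | 54.6% | 1.4 points | 66.5 | 12.4% | 95% |
| 20% | 52.9% | 3.1 points | 61.0 | 13.0% | 93% |
| 30% | 51.0% | 5.0 points | 55.3 | 13.7% | 90% |
| 40% | 48.8% | 7.2 points | 49.6 | 14.4% | 85% |

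Dialysis secondary patency (true 55% at 2 years) gives gaps of 1.4, 3.1, 5.0 and 7.3 points.

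**4. Hazard shape.** With Weibull failure times and e = 30%, the PAD gap is 6.5 points for early failures (shape 0.5) and 3.4 points for late failures (shape 2).

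**5. Aortic primary patency.** Exit is taken as death at the lower planning figure, so e = 1 − 0.33 = 67%. The documents give no patency rate, so 75%, 85% and 95% are assumptions.

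| Assumed patency | J | F | Evaluable: 65(J+F) | Exclusion reads | Gap |
|---|---|---|---|---|---|
| 75% | 0.2475 | 0.1550 | 26.2 | 61.5% | 13.5 points |
| 85% | 0.2805 | 0.0920 | 24.2 | 75.3% | 9.7 points |
| 95% | 0.3135 | 0.0304 | 22.4 | 91.2% | 3.8 points |

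**6. If exits and failures share patient risk.** Gamma frailty with variance v (assumed), PAD margins as above:

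- l = (S^−v − 1)/v, m = ((1 − e)^−v − 1)/v, A = 1 + v(l + m)
- Kaplan-Meier limit = A^(−l/(v(l+m)))
- exclusion = J/(J+F), with J = A^(−1/v) and F = l/(l+m) × (1 − J)

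| v | Error at e = 10/20/30/40%: Kaplan-Meier | Exclusion |
|---|---|---|
| 0.5 | +0.7/+1.4/+2.3/+3.3 points | −0.6/−1.2/−2.0/−2.9 points |
| 1.0 | +1.1/+2.3/+3.8/+5.6 points | 0 throughout |

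Under shared risk the two estimates still differ, and Kaplan-Meier is not the closer one.

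**The case against.** - **The text points to the binomial.** True, and because SAP 8.1 is only a minimum list, the lack of a binomial table there proves little. But the binomial itself has no rule for event-free exits, so choosing it does not fix the result.
- **Exclusion is only one reading.** This stands. Missing is described as an outcome that cannot be determined, the endpoints are worded as running through the horizon, and protocol 10.6.2 includes everyone eligible. A patient who died with a patent graft could be read as having a known status. A reader might infer that the plan makes patency read low; that holds only if event-free exits are excluded, earlier failures are kept and exits are independent.
- **Kaplan-Meier is no safer under shared risk.** This also stands (step 6). Independence cannot be checked from the documents, so which estimate should lead is partly a judgement.
- **Explant is a weak example of an event-free exit.** Agreed. Dialysis secondary patency runs to access abandonment, so an explant may itself be the failure.
- **Gaps are partly covered.** Protocol 5.10 fills a missed last visit from later visits, and collects safety data, through relatives or the general practitioner where consent is waived. That reduces missing visits but does not classify a death or a transplant. The deferred specifications may hold the rule, but they are not in these documents.
- **The study is descriptive.** No hypothesis or decision threshold is printed. This limits severity; it does not remove the ambiguity.

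**Conclusion.** The concern holds as one of definition: for each cohort the primary performance result has two planned estimators, no ranking and no status rule for event-free exits. For PAD at an assumed 30% exit probability, the readings of one dataset run from 39% to 62%, about 23 points, against a planned half-width of 12%. Exclusion alone differs from Kaplan-Meier by 5.0 points (3.4 to 6.5 by hazard shape). At 10% exits the gap is about 1.4 points and coverage is intact. Aortic primary patency is most exposed, with about 22 to 26 of 65 subjects usable under exclusion. That range needs both the lower planning survival figure and an assumed patency; it does not follow from 33% survival alone, and 33% is a floor.

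Three stronger inferences are not supported: that the plan biases patency downward, that Kaplan-Meier is necessarily the correct estimate, and that the defect must block a descriptive registry with no printed decision rule. All-cause survival is not distorted by deaths, since death is the event. This should be fixed before the data are analysed.

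**What to change.** Amend SAP 5.0 i) and ii) and protocol 10.1, 10.3, 10.6.2, 10.6.4 and 10.6.5 to name one primary estimate per endpoint:

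1. For patency, survival and limb endpoints, lead with the planned Kaplan-Meier estimate at the 5-, 2- or 1-year landmark, with a named 95% interval method (for example log-log Greenwood). Censor event-free subjects at last contact, death (unless death is the event) or transplant, and state the independent-censoring assumption.
2. State for each endpoint whether explant is an event.
3. For device-related infection, seroma and adverse event endpoints, name one primary estimate and say how death is treated.
4. Report the exact binomial among known-status subjects beside it as a sensitivity result, with the number evaluable, and add it to SAP 8.1.
5. State in SAP 2.6 and protocol 10.2 that the 12% half-width assumes all 72 or 65 subjects are evaluable.

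**Cost.** A wording amendment with ethics committee approval (protocol 6.6), and a lead interval that is no longer exact. Event and reintervention dates are already collected (protocol 9.1.3 and 5.9). The forms must be checked for the date of occlusion without reintervention and the date of access abandonment, which protocol 5.8.2 does not list.
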